### **Multiplicity**

No correction to the type I error rate will be applied to account for the primary and secondary endpoints. Accordingly, all analyses will utilize a two-sided alpha=0.05 level of significance with exception of the primary analysis. For the primary analysis, the final alpha level will be determined by the alpha spending function as defined in the following section.

### **Interim Analysis**

A partially blinded interim analysis will be conducted when 40% of the planned participants complete the 90 day outcome assessment (i.e., after the 100th participant completes the 90 day outcome). The O'Brien-Fleming-like alpha spending function will be used to determine the final alpha level. At time of study planning, 40% information fraction results in an interim stopping p-value of <0.00079. This value may vary slightly depending on the final data included in interim analysis. For partial blinding, the actual treatment codes will be replaced by generic "Treatment A" and "Treatment B" labels by the unblinded statistician for the DSMB's review. In the event a full unblinding of the study is desired, the DSMB will be able to request the actual treatment assignments from the unblinded study statistician.

## **7.3 Subject Population(s) for Analysis**

The subject populations whose data will be subjected to the study analysis both for the primary efficacy and safety analyses will include all randomized population under the intention to treat principle. Any subject randomized into the study, regardless of whether they received study drug will be included in the primary efficacy analysis provided the participant does not withdraw consent for use of any data collected in the course of the study or as otherwise required by institutional review board determination.

The per protocol analysis set will also be utilized for exploratory analyses. For this analysis, the participant will be expected to have obtained all outcome measurements over the 90 days along with >80% compliance with medication. Furthermore, the participant will need to not have a three day period (6 half-lives of apixaban) with no study medication. We will also perform a “full analysis set” and an “on-treatment” analysis for the study outcomes. For the purpose of this study, the full analysis set will be determined in accordance with ICH E9 guidelines. The on-treatment analysis data set will include subjects who are randomized to study and take at least one dose of study medication.

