## 1.2 Investigational Agent

Apixaban (Eliquis) is an oral direct factor Xa inhibitor which impairs coagulation by inhibiting the conversion of prothrombin to thrombin. It does not require antithrombin for antithrombotic activity and inhibits both free and clot-bound FXa. Apixaban has a half-life of about 12 hours and thus is dosed twice-daily. Bioavailability is approximately 50%, for doses up to 10 mg, after oral dosing with maximum concentrations at 4 hours post ingestion. The pharmacokinetics are linear and plasma protein binding in humans is high at nearly 90% with a volume of distribution of approximately 20 liters. Apixaban is metabolized in the liver mainly via CYP3A4 pathway. Renal excretion accounts for about 27% of total clearance. Approximately 25% of the drug is eliminated in the feces. This drug is not dialyzable due to its high plasma protein binding (the systemic exposure of apixaban is 14% lower for patients on dialysis when compared to not on dialysis). Apixaban is currently FDA approved to reduce the risk of stroke and systemic embolism in patients with nonvalvular atrial fibrillation, for the treatment of DVT and PE, and for the reduction in the risk of recurrent DVT and PE following initial therapy and for the prophylaxis of deep vein thrombosis (DVT), which may lead to pulmonary embolism (PE), in patients who have undergone hip or knee replacement surgery.

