#### 6.2 Surveillance and Follow up.

Following randomization, subjects will be assigned to either active treatment with apixaban or placebo control for a total of 90 days. Each subject will then undergo follow up ultrasound imaging at 7 days (+/- 2 days), 14 days (+/- 2 days) and 90 days (+/- 7 days). This ultrasound imaging study will focus on venous thrombus propagation into the proximal venous segments. At each follow up, all venous segments of the involved lower extremity will be imaged. This imaging should be performed at a site participating in this research project. Patients will be called at Days 30 & 60 (+/- 7 days) to check their health status, adverse reactions and medication compliance.

Patients will be instructed to report to the clinic immediately if they had any bleeding or symptoms of recurrent deep-vein thrombosis, pulmonary embolism, or both. All suspected episodes of recurrent thrombosis will be investigated with the use of objective tests, according to prespecified diagnostic algorithms. At 3 months (+/- 7 days), patients will return for a routine clinically indicated ultrasound and clinical assessment.

Study Activity	Day 0	Day 7 (± 2 days)	Day 14 (± 2 days)	Day 30 (± 7 days)	Day 60 (± 7 days)	Day 90 (± 7 days)
Informed consent	X					
History	X					
Concurrent meds	X	X	X	X	X	X

Collect data from clinical physical exam (Ht, Wt, BSA, VS)	X					
Collect Lab Values (CBC, creatinine, ALT/AST) a	X a					
Adverse event evaluation		X	X	X	X	X
B-HCG	X b					
Drug dispensing and collection of any unused drug	X					X
Ultrasound c	X	X	X			X
Telephone survey (appendix A)				X	X	

a = Collect data from clinical testing in the last 4 weeks.

b = Women of child bearing potential only. If not done clinically in the last 2 weeks.

c = The baseline ultrasound will be requested and performed by the provider caring for the patient. This will be a clinically indicated study and will not be repeated for study purposes. This US will serve as the baseline imaging study for trial purposes.

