## Appendix A. Telephone Script:

**Protocol Title:** A Phase IV, Randomized, Double Blind Study Evaluating the Safety and Efficacy of Apixaban in Subjects with Calf Vein Thrombosis

**Principal Investigator:** [name]

Completed By: \_\_\_\_\_

Date: \_\_\_\_\_

Circle One: Day 7      Day 14      Day 30      Day 60      Day 90

"Good morning/afternoon. This is \_\_\_\_\_ calling from Mayo Clinic Rochester/Eau Claire/La Cross. May I speak to \_\_\_\_\_?" **(If participant is there proceed to the following)**

"I would like to ask you a few questions regarding your blood thinner medication, you are taking for the clinical trial in which you have been enrolled. This will allow us to gather very important information about the safety and benefit of using this medication in treating and preventing blood clots."

I would like to ask these questions related to our study after confirming your name:

---

1. Since your last visit, have you missed any doses of your blood thinner medication?  
\_\_\_\_ Yes,  
If yes, approximately how many doses do you estimate that you have missed? \_\_\_\_  
\_\_\_\_ No, I have not missed any doses of medication
2. Since your last visit, have you had another blood clot problem?  
\_\_\_\_ Yes, a DVT  
\_\_\_\_ Yes, a PE  
\_\_\_\_ Both a DVT and a PE  
\_\_\_\_ Yes, something else (e.g. an arterial clot)  
\_\_\_\_ No, I have not had any more clots.
3. While you have been taking this medication as recommended, have you experienced any major bleeding which required hospitalization or blood transfusion?  
\_\_\_\_ Yes  
If yes, please describe: \_\_\_\_\_  
\_\_\_\_ No
4. While you have been taking this medication as recommended, have you experienced any bleeding other than from injury?  
\_\_\_\_ Yes,  
If yes, please describe \_\_\_\_\_  
\_\_\_\_ No

5. Which of the following best applies to your current activity rating:

- A.  Fully active, able to carry on all pre-disease performance without restriction.
- B.  Restricted in physically strenuous activity, but able to walk and to carry out work of a light or sedentary nature (for example, light house work, or office work).
- C.  Able to walk and capable of all self-care but unable to carry out any work activities. Up and about more than 50% of waking hours.
- D.  Capable of only limited self-care, confined to bed or chair more than 50% of waking hours.
- E.  Completely disabled. Cannot carry on any self-care. Totally confined to bed or chair.

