### Pain assessment

On a scale of 0 – 10, what is your current pain level for the involved leg with the blood clot? (circle one)

0 1 2 3 4 5 6 7 8 9 10

Has patient had a documented recurrent venous thrombosis confirmed by imaging? (check one)

1  Yes 2  No

If yes: Date diagnosed: (mm/dd/yyyy) \_\_\_\_/\_\_\_\_/\_\_\_\_

Pulmonary Embolism (check one) 1  Yes 2  No

Lower extremity deep vein thrombosis (check one) 1  Yes 2  No

Upper extremity deep vein thrombosis (check one) 1  Yes 2  No  
(jugular, innominate, subclavian, axillary, brachial)

Splanchnic vein thrombosis (check one) 1  Yes 2  No  
(hepatic, portal, splenic, mesenteric, renal, gonadal)

Cerebral vein thrombosis 1  Yes 2  No

Fatal PE: (check one) 1  Yes 2  No

Was the VTE recurrence: (check one) 1  Symptomatic 2  Incidental

How was the thrombus confirmed?

1  Ultrasound 2  CT 3  MRI 4  VQ scan 5  Surgery 6  Autopsy

Arterial clot: (check one) 1  Yes 2  No

If Yes, (check all that apply)  MI  
 TIA/Stroke  
 Peripheral embolism

Has patient had a major bleed? (check one) 1  Yes 2  No

If Yes, date of major bleed: (mm/dd/yyyy) \_\_\_\_/\_\_\_\_/\_\_\_\_-\_\_\_\_

If Yes (check all that apply)  Intracranial (intracerebral (hemorrhagic stroke), subarachnoid, subdural)

Intraspinal/epidural

Intraocular

Intraarticular

Intramuscular with compartment syndrome

Retroperitoneal

Pericardial

Fatal bleeding

GI

GU

Pulmonary

Other Specify: \_\_\_\_\_

Has patient had a clinically relevant non-major bleed? (check one) 1  Yes 2  No

If Yes, date of clinically relevant non-major bleed: (mm/dd/yyyy) \_\_\_\_/\_\_\_\_/\_\_\_\_-\_\_\_\_

If Yes, what were the consequences (check all that apply)

Required medical intervention

Unscheduled contact with health care team

Temporary cessation of study treatment

Has patient had a minor bleed? (check one) 1  Yes 2  No

If Yes, date of minor bleed: (mm/dd/yyyy) \_\_\_\_/\_\_\_\_/\_\_\_\_-\_\_\_\_

Last Date (any modality of) protocol therapy was given: (mm/dd/yyyy) \_\_\_\_/\_\_\_\_/\_\_\_\_-\_\_\_\_  
(date of last treatment dose on this study or date decision made to stop protocol treatment)

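### The on-treatment set in 7.3 has no end of exposure, and the per-protocol three-day gap rule cannot be fully verified from the forms shown and, read literally, drops patients with an efficacy event

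*Combined protocol and SAP*

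**What the plan says.** Section 7.3 makes intention to treat the basis of the primary efficacy analysis and adds further sets.

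- **Per-protocol (exploratory).** Three conditions: "the participant will be expected to have obtained all outcome measurements over the 90 days", ">80% compliance with medication", and the gap rule, "Furthermore, the participant will need to not have a three day period (6 half-lives of apixaban) with no study medication". No formula, denominator or data source is given for compliance.
- **On-treatment.** "The on-treatment analysis data set will include subjects who are randomized to study and take at least one dose of study medication". No window after the last dose is stated.

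The exposure data specified are:

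- the telephone script (Appendix A), which asks per interval since the last visit: "If yes, approximately how many doses do you estimate that you have missed";
- the schedule in 6.2, where the row "Drug dispensing and collection of any unused drug" is marked at Day 0 and Day 90 only;
- the follow-up CRF (Appendix B2), with the item "Last Date (any modality of) protocol therapy was given", whose note allows the date of the decision to stop instead of the date of the last dose;
- on the same CRF, a tick box for temporary cessation under clinically relevant non-major bleeding, with no stop or restart date.

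Section 4.4.1 stops study drug and starts another therapeutic anticoagulant after a thrombotic endpoint. After a clinically relevant non-major bleed it pauses study drug and allows a restart.

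**The concern.** A reader will expect an on-treatment analysis to describe events under study drug, and a per-protocol analysis to describe patients who adhered. As defined, the on-treatment set reuses the at-least-one-dose criterion of the safety analysis in 7.2.1.3. Section 7.2 limits events only by the 3-month period and ignores timing within it. A bleed on the alternate anticoagulant is therefore counted to the randomized arm. Most switching is expected in the placebo arm, so the direction is to understate any bleeding excess with apixaban.

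The per-protocol set has two weaknesses. Whether an interior three-day gap occurred may be undecidable from the data specified. And because study drug stops at a thrombotic event, the adherence rules can exclude the patients who had the outcome, mostly from the placebo arm.

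**Working it through.** **1. The plan's own figure.** Section 1.2 states: "Apixaban has a half-life of about 12 hours and thus is dosed twice-daily". Three days is 72 h, and 72/12 = 6 half-lives, so the figure in 7.3 reproduces. At twice-daily dosing a three-day gap is 6 consecutive doses.

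**2. Can the 80% rule stand in for the gap rule?** Inputs: 90 days in total (6.2); 4 tablets a day for 7 days, then 2 a day (5.5).

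- Tablets due: 7 × 4 + 83 × 2 = 194.
- 38 missed: 156/194 = 80.4%, passes. 39 missed: 155/194 = 79.9%, fails.
- 38 tablets at 2 a day = 19 maintenance days.
- One three-day gap: 188/194 = 96.9% in maintenance, 182/194 = 93.8% in the first week.

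If the regimen is read as 7 days plus a further 90 days (3.1 and 5.2 say 3 months after the first week), 28 + 180 = 208 tablets are due. Then 41 may be missed (167/208 = 80.3%), about 20 days. The conclusion is the same: the compliance rule does not see a three-day gap.

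**3. Does a missed-dose count identify a gap?**

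- Fewer than 6 missed: a 6-dose run is impossible, so the rule is decided, if the count is reliable.
- 12 of 180 missed: the chance of a run of 6 or more is about 0 if the misses are scattered at random (simulated) and 1 if they are consecutive.
- 36 of 180 missed: 0.7% if scattered, 1 if consecutive.
- 38 of the 60 doses in a 30-day interval missed: 84% even if scattered, so a very long gap usually shows in the count.
- A permanent stop can be dated from the CRF, subject to the decision-date alternative.

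What stays open is the interior gap with 6 or more doses missed in an interval.

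**4. Person-time after switching.** Inputs: 125 per arm; planning rates 10% and 1.6% (7.1). Assumptions: every patient with an event switches, with 20 to 83 days remaining. The upper end is an event at Day 7, since 90 − 7 = 83.

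- Switchers: 0.10 × 125 = 12.5 placebo; 0.016 × 125 = 2 apixaban.
- Placebo person-time: 125 × 90 = 11,250 days.
- Placebo days on the alternate anticoagulant: 12.5 × 20 = 250 (2.2%) to 12.5 × 83 = 1,037.5 (9.2%).
- Apixaban arm: 2 × 20 = 40 (0.4%) to 2 × 83 = 166 (1.5%).

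For bleeds, take the 4% reported on LMWH in the CACTUS trial (1.1) and assume that it accrued over the 42 treatment days. Placebo-arm bleeds after switching: 250/42 × 0.04 = 0.24 to 1,037.5/42 × 0.04 = 0.99. With that trial's 0.8% for major bleeds: 0.05 to 0.20.

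**5. What the per-protocol rules do to patients with events.** Take a fully adherent patient whose drug stops at a thrombotic event, with compliance measured against the 194 tablets due over 90 days.

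- Stop at Day 14: 28 + 7 × 2 = 42; 42/194 = 22%.
- More than 80% needs 156 tablets: 28 + 2 × 64 = 156, so drug must continue to Day 7 + 64 = 71.
- Gap rule: a stop before about Day 87 (90 − 3) leaves three days or more without study drug.

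A patient who dies early also fails the condition on complete outcome measurements.

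**The case against.** The strongest reply is that little rests on these sets. The per-protocol analysis is labelled exploratory, the primary analysis is intention to treat, and no alpha or stopping rule depends on either set. That stands, and it sets the severity.

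The data are also richer than the items above suggest. Missed doses are asked per interval, and the script header lists Days 7, 14 and 90 as well as 30 and 60, although the schedule marks calls only at Days 30 and 60. Section 5.8.3 asks for regular drug reconciliation. The CRF dates the bleed beside the cessation tick box, section 8 requires follow-up of non-serious adverse events that interrupt study drug, and concurrent medication is collected at every contact. These may allow partial reconstruction. None specifies the start and stop dates of an interruption. The appended forms may not be the full set, so the claim is only that these documents do not specify the dates.

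Three stronger readings are tempting and are not supported:

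- **That exposure is not measured, or that the gap rule can never be applied.** Aggregate compliance is computable from returned tablets, fewer than 6 missed doses excludes a gap, and a terminal stop can be dated.
- **That patients with long gaps stay in the per-protocol set.** As written they are excluded; the difficulty is verification.
- **That the bleeding comparison is materially distorted.** The expected shift is about one event or fewer, and the safety analysis in 7.2.1.3 shares the feature.

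**Conclusion.** The point holds in limited form and is minor.

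- **On-treatment.** The set has no end of exposure, so it cannot isolate events under study drug. The affected share is about 2% to 9% of placebo patient-days, probably one bleed or fewer. This rests on the planning rates, on every patient with an event switching, on the assumed days remaining, and on a borrowed bleeding rate.
- **Gap rule.** Its arithmetic is right. It is unverifiable only for interior gaps with 6 or more doses missed in an interval, and the 80% rule does not fill that hole.
- **Loss of events.** Read literally, the per-protocol rules remove most patients with an efficacy event, from a pool of about 12.5 placebo and 2 apixaban. This assumes that compliance is measured over the full 90 days and that most events come before the last weeks. Section 2 reports the current view that propagation occurs within two weeks, but also says that this is unvalidated. Events first found at the Day 90 ultrasound could stay in. Of the weaknesses here, this one most affects how the per-protocol result could be read.

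The intention-to-treat result does not change under any of these.

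**What to change.** 1. **Section 7.3, on-treatment.** Count events from first dose to actual last dose plus a pre-stated lag, ending at the start of any other therapeutic anticoagulant. A lag of 3 days matches the protocol's own 6 half-lives. Otherwise rename the set, since at-least-one-dose membership alone does not describe exposure.
2. **Follow-up CRF and telephone script.** Add start and stop dates of any interruption, the actual last-dose date as a field separate from the decision date, and the start date of any other anticoagulant.
3. **Section 7.3, per-protocol.** Assess compliance and the gap rule only up to the first efficacy event or death, and state the compliance denominator.

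A tablet count at the existing Day 7 and Day 14 visits is optional; it would show adherence in the lead-in week separately.

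The cost is a few extra fields, a few sentences in 7.3, and slightly smaller exploratory sets. The dates need to be collected during the trial, because they cannot be reliably reconstructed afterwards.

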## 8 Safety and Adverse Events

### 8.1 Definitions

**1. Adverse Events.** An Adverse Event (AE) is defined as any new untoward medical occurrence or worsening of a preexisting medical condition in a clinical investigation participant administered study drug and that does not necessarily have a causal relationship with this treatment. An AE can therefore be any unfavorable and unintended sign (such as an abnormal laboratory finding), symptom, or disease temporally associated with the use of investigational product, whether or not considered related to the investigational product. The causal relationship to study drug is determined by a physician and should be used to assess all adverse events (AE). The causal relationship can be one of the following:

**Related:** There is a reasonable causal relationship between study drug administration and the AE.

**Not related:** There is not a reasonable causal relationship between study drug administration and the AE.

The term "reasonable causal relationship" means there is evidence to suggest a causal relationship.

Adverse events can be spontaneously reported or elicited during open-ended questioning, examination, or evaluation of a subject. (In order to prevent reporting bias, subjects should not be questioned regarding the specific occurrence of one or more AEs.)

**2. Serious Adverse Events.** Serious Adverse Event (SAE) is any untoward medical occurrence; results in death; is life-threatening (defined as an event in which the participant was at risk of death at the time of the event; it does not refer to an event which hypothetically might have caused death if it were more severe); requires inpatient hospitalization; or causes prolongation of existing hospitalization (see NOTE below); results in persistent or significant disability/incapacity; is a congenital

anomaly/birth defect; is an important medical event (defined as a medical event(s) that may not be immediately life-threatening or result in death or hospitalization but, based upon appropriate medical and scientific judgment, may jeopardize the subject or may require intervention [eg, medical, surgical] to prevent one of the other serious outcomes listed in the definition above.) (Examples of such events include, but are not limited to, intensive treatment in an emergency room or at home for allergic bronchospasm; blood dyscrasias or convulsions that do not result in hospitalization).

Suspected transmission of an infectious agent (eg, pathogenic or nonpathogenic) via the study drug is an SAE.

Although pregnancy, overdose, adverse events of special interest, and cancer are not always serious by regulatory definition, these events must be handled as SAEs. Any component of a study endpoint that is considered related to study therapy should be reported as an SAE (eg, death is an endpoint, if death occurred due to anaphylaxis, anaphylaxis must be reported).

The following hospitalizations are not considered SAEs in BMS clinical studies: a visit to the emergency room or other hospital department < 24 hours, that does not result in admission (unless considered an important medical or life-threatening event); elective surgery, planned prior to signing consent admissions as per protocol for a planned medical/surgical procedure routine health assessment requiring admission for baseline/trending of health status (eg, routine colonoscopy); medical/surgical admission other than to remedy ill health and planned prior to entry into the study. Appropriate documentation is required in these cases.

Admission encountered for another life circumstance that carries no bearing on health status and requires no medical/surgical intervention (eg, lack of housing, economic inadequacy, caregiver respite, family circumstances, administrative reason).

**3. Adverse Events of Special Interest.** In this study, the following adverse events are to be reported to BMS as serious events, regardless of whether these reports are classified as serious or unexpected: Potential or suspected cases of liver injury including but not limited to liver test abnormalities, jaundice, hepatitis or cholestasis.

**4. Pregnancy.** If, following initiation of the investigational product, it is subsequently discovered that a study participant is pregnant or may have been pregnant at the time of investigational product exposure, including during at least 5 half-lives after product administration, the investigational product will be permanently discontinued in an appropriate manner (eg, dose tapering if necessary for participant).

The investigator must immediately notify [[contact]](mailto:[contact]) of this event via, MedWatch or appropriate Pregnancy Surveillance Form in accordance with SAE

reporting procedures. Protocol-required procedures for study discontinuation and follow-up must be performed on the participant. Follow-up information regarding the course of the pregnancy, including perinatal and neonatal outcome and, where applicable, offspring information must be reported on the, MedWatch or appropriate Pregnancy Surveillance Form. Any pregnancy that occurs in a female partner of a male study participant should be reported to BMS. Information on this pregnancy will be collected on the Pregnancy Surveillance Form. In order for Sponsor or designee to collect any pregnancy surveillance information from the female partner, the female partner must sign an informed consent form for disclosure of this information.

**5. Overdose.** An overdose is defined as the accidental or intentional administration of any dose of a product that is considered both excessive and medically important. All occurrences of overdose must be reported as an SAE.

**6. Non-serious Adverse Event.** Non-serious Adverse Events (AE) are to be provided to BMS in aggregate via interim or final study reports as specified in the agreement or, if a regulatory requirement [eg, IND US trial] as part of an annual reporting requirement.

Non-serious AE information should also be collected from the start of a placebo lead-in period or other observational period intended to establish a baseline status for the subjects. A non-serious adverse event is an AE not classified as serious.

**7. Serious Adverse Event Collection and Reporting.** Following the subject's written consent to participate in the study, all SAEs, whether or not related to the BMS product under study, must be collected, including those thought to be associated with protocol-specified procedures. SAEs must be recorded on CIOMS or FDA MedWatch 3500A Form and reported to BMS (or designee) within 1 business day to comply with regulatory requirements. A form should be completed for any event where doubt exists regarding its status of seriousness. Although overdose and cancer are not always serious by regulatory definition, these events should be recorded on a form and reported to BMS within 1 business day.

All SAEs must be reported by confirmed facsimile (fax) transmission or reported via electronic mail to:

SAE Email Address: [contact]

SAE [contact]

If only limited information is initially available, follow-up reports may be required. For studies capturing SAEs through electronic data capture (EDC), electronic submission is the required method for reporting. The paper forms should be used and submitted immediately, only in the event the electronic system is unavailable for transmission. When paper forms are used, the original paper forms are to remain on site.

If it is discovered a patient is pregnant or may have been pregnant at the time of exposure to the BMS product under study, the pregnancy, AEs associated with maternal exposure and pregnancy outcomes must be recorded on a Pregnancy

Surveillance Form and reported to BMS (or designee) within 1 business day by confirmed fax or reported via electronic mail to [contact]. If only limited information is initially available, follow-up reports may be required. The original BMS forms are to remain on site. Follow-up information should be obtained on pregnancy outcomes for one year following the birth of the offspring. Any pregnancy that occurs in a female partner of a male study participant should be reported to BMS. Information on this pregnancy will be collected on the Pregnancy Surveillance Form.

**8. Non-serious Adverse Event Collection and Reporting.** The collection of non-serious AE information should begin at initiation of study drug. All non-serious adverse events (not only those deemed to be treatment-related) should be collected continuously during the treatment period and for a minimum of 30 days following the last dose of study treatment.

Non-serious AEs should be followed to resolution or stabilization, or reported as SAEs if they become serious. Follow-up is also required for non-serious AEs that cause interruption or discontinuation of study drug and for those present at the end of study treatment as appropriate.

Nonserious Adverse Events are provided to BMS via annual safety reports (if applicable), and interim or final study reports.

**9. SAE Reconciliation.** The investigator will reconcile the clinical database SAE cases transmitted to BMS Global Pharmacovigilance (GPV&E). Frequency of reconciliation will be done every three months and once prior to study database lock. BMS GPV&E will e-mail upon request from the investigator, the GPV&E reconciliation report. Requests for reconciliation should be sent to [[contact]](mailto:[contact]). The data elements listed on the GPV&E reconciliation report will be used for case identification purposes. If the investigator determines a case was not transmitted to BMS GPV&E, the case will be sent immediately.

